9.1.2 Withdrawal of informed consent

Subjects may voluntarily withdraw consent to participate in the study for any reason at any time. Withdrawal of consent occurs only when a subject:

- Does not want to participate in the study anymore and
- Does not allow further collection of personal data

In this situation, the investigator should make a reasonable effort (eg telephone, e-mail, letter) to understand the primary reason for the subject's decision to withdraw his/her consent and record this information.

Further attempts to contact the subject are not allowed unless safety findings require communicating or follow-up.

All efforts should be made to complete the assessments prior to study withdrawal. A final evaluation at the time of the subject's study withdrawal should be made as detailed in the assessment table.

Novartis will continue to keep and use collected study information (including any data resulting from analysis of a subject's samples until the time of withdrawal) according to the applicable law.

9.1.3 Lost to follow-up

For subjects whose status is unclear because they fail to appear for study visits without stating an intention to discontinue or withdraw, the investigator must show "due diligence" by documenting in the source documents steps taken to contact the subject, eg dates of telephone calls, registered letters, etc. A subject should not be considered as lost to follow-up until due diligence has been completed or until the end of the study.

9.1.4 Early study termination by the sponsor

The study can be terminated by Novartis at any time for any reason. This may include reasons related to the benefit/risk assessment of participating in the study, practical reasons (including slow enrollment), or for regulatory or medical reasons. In taking the decision to terminate, Novartis will always consider the subject welfare and safety. Should early termination be necessary, subjects must be seen as soon as possible (provide instruction for contacting the subject, when the subject should stop taking drug, when the subject should come for a final visit) and treated as a prematurely withdrawn subject. The investigator may be informed of additional procedures to be followed in order to ensure that adequate consideration is given to the protection of the subject's interests. The investigator or sponsor depending on the local regulation will be responsible for informing IRBs / IECs of the early termination of the trial.

9.2 Study completion and post-study treatment

Study completion is defined as when the last subject finishes their End of Study Visit, and any repeat assessments associated with this visit have been documented and followed-up appropriately by the Investigator, or in the event of an early study termination decision, the date of that decision.

10 Safety monitoring and reporting

10.1 Definition of adverse events and reporting requirements

10.1.1 Adverse events

An adverse event (AE) is any untoward medical occurrence (eg, any unfavorable and unintended sign (including abnormal laboratory findings), symptom or disease) in a subject or clinical investigation subject after providing written informed consent for participation in the study. Therefore, an AE may or may not be temporally or causally associated with the use of a medicinal (investigational) product.

The investigator has the responsibility for managing the safety of individual subject and identifying adverse events.

Novartis qualified medical personnel will be readily available to advise on trial related medical questions or problems.

The occurrence of adverse events must be sought by non-directive questioning of the subject at each visit during the study. Adverse events also may be detected when they are volunteered by the subject during or between visits or through physical examination findings, laboratory test findings, or other assessments.

Adverse events must be recorded in the Adverse Events CRF under the signs, symptoms or diagnosis associated with them, accompanied by the following information (as far as possible) (if the event is serious refer to [Section 10.1.2](#)):

1. The severity grade includes the following:
 - mild: usually transient in nature and generally not interfering with normal activities
 - moderate: sufficiently discomforting to interfere with normal activities
 - severe: prevents normal activities
2. its relationship to the study treatment. If the event is due to lack of efficacy or progression of underlying illness (ie progression of the study indication) the assessment of causality will usually be 'Not suspected'. The rationale for this guidance is that the symptoms of a lack of efficacy or progression of underlying illness are not caused by the trial drug, they happen in spite of its administration and/or both lack of efficacy and progression of underlying disease can only be evaluated meaningfully by an analysis of cohorts, not on a single subject.
3. its duration (start and end dates) or if the event is ongoing, an outcome of not recovered/not resolved must be reported.
4. whether it constitutes a SAE (see [Section 10.1.2](#) for definition of SAE) and which seriousness criteria have been met.
5. action taken regarding with study treatment.

All adverse events must be treated appropriately. Treatment may include one or more of the following:

- no action taken (further observation only)
- Concomitant medication or non-drug therapy given.

6. its outcome
 - a. not recovered/not resolved;
 - b. recovered/resolved;
 - c. recovering/resolving,
 - d. recovered/resolved with sequelae;
 - e. fatal; or unknown

Conditions that were already present at the time of informed consent should be recorded in medical history source document of the subject.

Adverse events (including lab abnormalities that constitute AEs) should be described using a diagnosis whenever possible, rather than individual underlying signs and symptoms.

Adverse event monitoring should be continued for at least 30 days, following the injection.

Once an adverse event is detected, it must be followed until its resolution or until it is judged to be permanent (eg continuing at the end of the study), and assessment must be made at each visit

(or more frequently, if necessary) of any changes in severity, the suspected relationship to the interventions required to treat it, and the outcome.

Information about adverse drug reactions for the investigational drug can be found in the Investigator Brochure (IB).

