Period	A minor subdivision of the study timeline; divides phases into smaller functional segments such as screening, baseline, titration, washout, etc.
Personal Data	Subject information collected by the Investigator that is transferred to Novartis for the purpose of the clinical trial. This data includes subject identifier information, study information and biological samples.
Screen Failure	A subject who is screened but is not treated or randomized
Source Data	Source data refers to the initial record, document, or primary location from where data comes. The data source can be a database, a dataset, a spreadsheet or even hard-coded data, such as paper or eSource.
Study completion	Point/time at which the subject came in for a final evaluation visit or when study drug was discontinued whichever is later.
Study treatment	Any drug (or combination of drugs) administered to the study participants as part of the required study procedures; includes investigational drug(s), control(s) or non-investigational medicinal product(s)
Subject	An individual who has consented to participate in this study. The term Subject may be used to describe either a healthy volunteer or a patient.
Subject number	A unique number assigned to each subject upon signing the informed consent. This number is the definitive, unique identifier for the subject and should be used to identify the subject throughout the study for all data collected, sample labels, etc.
Variable	Information used in the data analysis; derived directly or indirectly from data collected using specified assessments at specified timepoints.

Withdrawal of consent (WoC)	Withdrawal of consent from the study is defined as when a subject does not want to participate in the study any longer, and does not want any further visits or assessments, and does not want any further study related contact, and does not allow analysis of already obtained biologic material
-----------------------------	-----------------------------------------------------------------------------------------------------------------------------------------------------------------------------------------------------------------------------------------------------------------------------------------------------

Amendment 1

Amendment rationale

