6.7.2 Instruction for prescribing and taking study treatment

The IVT injection will be carried out under controlled, aseptic conditions per local clinical practice. The study eye will be assessed before and after intravitreal injection to ensure that the procedure and/or the study treatment had not endangered the health of the eye. An IVT injection is contraindicated in subjects with active ocular-or periocular infections and in subjects with active intraocular inflammation; therefore, the investigator should verify that these conditions are not present in either eye (study and fellow eyes) prior to the injection.

All kits of study treatment will be recorded/databased. Date and time of every injection administered to the subject will be recorded in the eCRF.

Additionally, the conduct of IVT injections brolucizumab 6 mg PFS will be observed by an external team under observational protocol [REDACTED].

[REDACTED]

7 Informed consent procedures

Eligible subjects may only be included in the study after providing (witnessed, where required by law or regulation), IRB/IEC-approved informed consent.

If applicable, in cases where the subject's representative(s) gives consent (if allowed according to local requirements), the subject must be informed about the study to the extent possible given his/her understanding. If the subject is capable of doing so, he/she must indicate agreement by personally signing and dating the written informed consent document.

Informed consent must be obtained before conducting any study-specific procedures (eg all of the procedures described in the protocol). The subject will also need to consent that the injection procedure and observation is video recorded. The process of obtaining informed consent must be documented in the subject source documents.

Novartis will provide to investigators in a separate document a proposed informed consent form that complies with ICH/GCP guidelines and regulatory requirements and is considered appropriate for this study. Any changes to the proposed consent form suggested by the investigator must be agreed by Novartis before submission to the IRB/IEC.

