8.4 Safety

Safety evaluation will include ocular and non-ocular assessments (eg vital signs, IOP, slitlamp and ophthalmoscopy) and will be performed according to the clinical practice. Any clinically significant changes should be reported as AEs.

For details on AE collection and reporting, refer to [Section 10.1.1](#).

The End of Study visit after 7 days (\pm 2) will be done at the site. The ocular assessments like slitlamp and ophthalmoscopy will be recorded in the source document and IOP will be entered in the eCRF. The non-ocular assessment (vital signs) will be recorded in the eCRF.

Additionally, a follow-up phone call 30 days after the End of Study Visit will be performed for subjects with any ongoing AEs at the End of Study Visit. Any occurred adverse events in this period should be collected in the source, and SAEs must be reported to Novartis safety according instructions in [Section 10.1.3](#).

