12.4.2 Statistical model, hypothesis, and method of analysis

No formal hypothesis tests will be performed in this study. All safety analyses will be performed using the FAS.

Adverse events

The number (and percentage) of subjects with treatment-emergent adverse events (events started after the single dose of study treatment or events present prior to start of study treatment but which increased in severity based on preferred term) will be summarized in the following ways:

- by treatment, primary system organ class and preferred term
- by treatment, primary system organ class, preferred term and maximum severity
- by treatment, Standardized MedDRA Query (SMQ) and preferred term

Separate summaries will be provided for study treatment related adverse events, death, serious adverse events, other significant adverse events leading to discontinuation of the study. Separate presentations will be provided related to ocular events in the study eye and fellow eye and systemic events. Additional summaries will be provided by severity and causality (separately assessed for the injection procedure and the drug). Subject listings of all adverse events will be provided. Deaths and other serious or clinically significant non-fatal adverse events will be listed separately.

A subject with multiple adverse events within a primary system organ class is only counted once towards the total of the primary system organ class.

Ophthalmic examinations

Pre-injection and post-injection IOP measurements will be listed.

Vital signs

All vital signs data will be listed by subject and, if ranges are available, abnormalities will be flagged with thresholds representing clinical relevant abnormality.

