13.4 Quality Control and Quality Assurance

Novartis maintains a robust Quality Management System (QMS) that includes all activities involved in quality assurance and quality control, to ensure compliance with written Standard Operating Procedures as well as applicable global/local GCP regulations and ICH Guidelines.

Audits of investigator sites, vendors, and Novartis systems are performed by auditors, independent from those involved in conducting, monitoring or performing quality control of the clinical trial. The clinical audit process uses a knowledge/risk based approach.

Audits are conducted to assess GCP compliance with global and local regulatory requirements, protocols and internal SOPs, and are performed according to written Novartis processes.

14 Protocol adherence

This protocol defines the study objectives, the study procedures and the data to be collected on study participants. Additional assessments required to ensure safety of subjects should be administered as deemed necessary on a case by case basis. Under no circumstances including incidental collection is an investigator allowed to collect additional data or conduct any additional procedures for any purpose involving any investigational drugs under the protocol, other than the purpose of the study. If despite this interdiction prohibition, data, information, observation would be incidentally collected, the investigator shall immediately disclose it to Novartis and not use it for any purpose other than the study, except for the appropriate monitoring on study participants.

Investigators ascertain they will apply due diligence to avoid protocol deviations. If an investigator feels a protocol deviation would improve the conduct of the study this must be considered a protocol amendment, and unless such an amendment is agreed upon by Novartis and approved by the IRB/IEC and health authorities, where required, it cannot be implemented.

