## **2.1.1 General definitions**

The term 'study treatment' refers to brolucizumab 6 mg (PFS).

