### **2.8.1 Adverse events**

AEs will be coded using MedDRA Version 21.1.

All AEs will be listed.

Summaries will include all treatment emergent AEs which are defined as AEs which start on or after the date of the injection of study treatment up until the patient discontinues or completes the study.

Analyses will be performed for ocular AEs for the study eye only and non-ocular AEs. Ocular and non-ocular AEs will be presented separately. Ocular AEs for the fellow eye will be listed only.

The number and percentage of subjects who reported treatment emergent AEs will be summarized by primary SOC and PT for:

- all AEs
- all AEs by maximum severity
- all AEs by investigator causality assessment (relationship to study treatment and/or study treatment administration procedure)
- AEs leading to study discontinuation
- all serious adverse events (SAE)

If a subject reports more than one AE with the same PT, the AE will be counted only once for that PT. If a subject reports more than one AE within the same primary SOC, the subject will be counted only once for that SOC.

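### Does the plan analyse an injection-procedure causality that investigators are never asked to record?

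*Protocol*

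**What the plan says.** Protocol 8.4 sends the reader elsewhere for AE collection: "For details on AE collection and reporting, refer to" Section 10.1.1. That section lists six things to record with each event: severity, causality, duration, seriousness, action taken and outcome. The causality item reads "its relationship to the study treatment. If the event is due to lack of efficacy or progression of underlying illness", and the guidance under it concerns the drug.

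The analysis text names two relationships. Protocol 12.4.2: "Additional summaries will be provided by severity and causality (separately assessed for the injection procedure and the drug". SAP 2.8.1, in its list of treatment-emergent summaries by SOC and PT: "all AEs by investigator causality assessment (relationship to study treatment and/or study treatment administration procedure".

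Study treatment is defined as a drug. The protocol glossary has "Any drug (or combination of drugs) administered to the study participants as part of the required study procedures", and SAP 2.1.1 says that the term "refers to brolucizumab 6 mg (PFS". Protocol 6.7.2 keeps injection and drug apart when it calls for the eye to be checked "to ensure that the procedure and/or the study treatment had not endangered the health of the eye".

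On the scope of the document, Protocol 14 says: "This protocol defines the study objectives, the study procedures and the data to be collected on study participants".

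**The concern.** The section that tells sites what to record has one causality item, and the sections that say what to analyse have two. Since study treatment is defined as the drug, the single item cannot be stretched to cover the injection. If sites recorded only what 10.1.1 lists, the procedure half of the causality summary would have no data, and rewording the SAP could not supply them.

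This would matter more here than in many studies. The only objective is the safety of brolucizumab delivered in the prefilled syringe, and the syringe changes preparation and delivery compared with the vial. There is no control arm, so no comparison between groups can help to tell drug effects from injection effects. The investigator's causality judgement is the one planned summary that tries to separate them. There is also a worry that an event due to the injection alone would be entered inconsistently across the approximately 3 sites, and that this would move the treatment-related incidence.

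**Working it through.** The plan gives no figure on this point, so the check is mainly a comparison of texts.

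**1. Items recorded.** Protocol 10.1.1 has six items. One concerns causality and none names the injection procedure. The only other relationship mentioned in 10.1.1 is to the interventions used to treat the event. SAE reporting in 10.1.3 also speaks only of study treatment. The omission from the recording list is real.

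**2. Items analysed.** Protocol 12.4.2 names two judgements and describes them as separately assessed. That wording reports an assessment that is made, not only a table that is planned. SAP 2.8.1 attributes the judgement to the investigator and names the same two relationships.

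**3. Do the texts contradict each other?** A contradiction would need 10.1.1 to say that its list is complete, or some passage to say that procedure causality is not assessed. Neither statement appears. Protocol 14 makes the protocol as a whole, not 10.1.1 alone, the definition of the data to be collected, and 12.4.2 belongs to that whole. Read together, the sections require two judgements, one of which is named in an inconvenient place.

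**4. What the SAP shows about the data.** Its document history records four changes made before database lock. One of them responds to what sites had entered on the eCRF, so the plan was being revised with collected data in view. SAP Section 4 declares seven departures from the protocol analyses: one from 12.2, two from 12.3 and four from 12.4.2 (1 + 2 + 4 = 7). Two of the four from 12.4.2 cut back AE outputs, namely the SMQ summary and the fellow-eye presentation. Procedure causality is not among the seven. Authors who listed those departures and kept the causality bullet probably expected the field to exist. This is an inference, not proof.

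**5. The possible numerical effect.** If k subjects have only a procedure-attributed event and sites enter it as related to study treatment, treatment-related incidence shifts by k/n. With n = 30, k = 1 gives 1/30 = 3.3 points, k = 2 gives 2/30 = 6.7 and k = 3 gives 3/30 = 10.0. Two things remove this as a measure of harm.

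- The documents give no value for k, and one subject in 30 is 3.3 points for any AE attribute.
- The calculation conflicts with the premise. If study treatment clearly excludes the procedure, an event due to the injection alone is simply not suspected for study treatment, and the shift is 0. A non-zero shift needs the term to be ambiguous, and in that case item 2 no longer clearly leaves the procedure out.

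**6. The primary endpoint.** Incidence of ocular and non-ocular AEs counts events whatever their cause. It does not depend on item 2.

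**The case for a change.** The strongest reply is that sites work from the recording section, not from the statistics section. Protocol 8.4 directs them to 10.1.1, and a judgement mentioned only under analysis methods may never reach the person completing the form. If the eCRF was built from 10.1.1, the procedure judgement would be missing and would have to be obtained by query or declared as not delivered. The SAP's and/or wording could also mean one combined category, which would differ from the separate assessment in 12.4.2 and would then belong in SAP Section 4.

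Part of this stands. The list in 10.1.1 is less complete than it could be, and 12.4.2 is an odd place to learn that a second judgement is made. The rest depends on a form that is not among the documents, and the SAP evidence points the other way. Even if the field were missing, queries before lock for about 30 subjects would be feasible, so the information would not necessarily be lost. As for the and/or wording, either reading presupposes that the procedure judgement exists, so it does not support the claim that none was recorded. SAP 2.8.1 also lists every AE, and in a study of this size individual attributions can be read from a listing if both were collected.

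**Conclusion.** The mismatch in wording is genuine, but it is a missing detail that the rest of the plan supplies. Protocol 12.4.2 states that both causalities are assessed, and SAP 2.8.1 uses both. An analyst would look for the two fields on the AE form in the ordinary course of programming the table and would report under Section 4 if one were absent. Writing the second relationship into 10.1.1 would make the protocol tidier and would alter no planned result.

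The extent is one unnamed item out of six, affecting one descriptive summary shown for two AE groups (ocular in the study eye, and non-ocular). There is no hypothesis test to disturb, and AE incidence is unaffected. The percentage-point shifts should carry no weight, since they rest on an assumed count and on a reading of study treatment that the concern itself rejects.

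This conclusion assumes that the eCRF holds a procedure-causality field. The documents make that likely but do not prove it. If it did not, the loss would be confined to the procedure part of that one summary.
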